3.1 Potential Risks and Benefits

The safety assessments of M2951 rely on data accumulated during product development and from data on other BTK inhibitors. Based on the nonclinical and clinical data available to date, the conduct of the trial is regarded as justifiable at the planned dose.

M2951, is being considered for the treatment of autoimmune diseases, including RA, SLE, and MS. To date, no efficacy data are available. However, because its mechanism of action directly targets both the production of autoantibodies and cellular effectors of end-organ injury, it is reasonable to anticipate that M2951 may represent a significant advance in the treatment of RA and other autoimmune diseases.

No identified risks or new potential risks have emerged from the first-in-human trial, Trial EMR200527-001. M2951 was well tolerated [REDACTED]

Important potential risks to subjects are based on nonclinical safety data of M2951 and clinical data on adverse drug effects associated with compounds of a similar pharmacological class. They include infection, leukopenia, thrombocytopenia, hemorrhage, gastrointestinal intolerance, renal toxicity, hepatocellular injury, atrial fibrillation, drug-drug interactions, and embryofetal toxicity. It is unknown whether there are additive risks of cytopenias and elevated transaminases when M2951 is given with MTX; however, these potential risks will be readily monitored.

Risk minimization measures inherent to early phase clinical trials are considered adequate for the proposed clinical trial in RA patients. An IDMC will be set up to continually review available safety and tolerability data and will be mandated to make immediate decisions regarding the conduct of the trial; no additional risk minimization measures are proposed.

The dose of M2951 (50 mg bid) selected for the proposed trial is well within the dose ranges studied in Trial EMR200527-001 and showed high levels of target occupancy in healthy volunteers.

Taking the above information into account, benefit-risk considerations support conduct of the proposed clinical trial EMR200527-0081 in patients with RA.

For full details, refer to the latest IB for further information about the nonclinical and clinical programs and Guidance for the Investigator.

This clinical trial will be conducted in compliance with the clinical trial protocol, ICH GCP guidelines, and any additional applicable regulatory requirements.

4 Trial Objectives

4.1 Primary Objective

To assess the efficacy of M2951 in subjects with active RA on stable MTX therapy, as measured by the American College of Rheumatology (ACR) 20% (ACR20) response rate over a duration of 84 days.

4.2 Key Secondary Objective

To assess the level of disease activity at 4 weeks in subjects with active RA as assessed by the percent change in high-sensitivity C-reactive protein (hsCRP) from Baseline to Day 29.

4.3 Other Secondary Objectives (during the double-blind period)

4.3.1 Safety

To assess the safety and tolerability of M2951 in subjects with active RA on stable MTX therapy from signing ICF until Safety Follow-up Visit, as assessed by the:

- Nature, incidence, and severity of TEAEs
- Changes from Baseline in vital signs and 12-lead electrocardiogram (ECG) data
- Changes from Baseline in standard hematology and chemistry laboratory parameters including liver function tests, amylase/lipase, and urinalysis.

4.3.2 Pharmacokinetics and Pharmacodynamics

To evaluate the PK and PD of M2951 in subjects with RA on stable MTX therapy, as assessed by:

- Pharmacokinetic parameters will include:
 - C_{max} , t_{max} , plasma concentration observed immediately before next dosing (C_{pre} [Day 29]), area under the concentration-time curve from time zero to 6 hours (AUC_{0-6h}), accumulation ratio for AUC_{0-6h} ($R_{acc[AUC_{0-6h}]}$), and accumulation ratio for C_{max} ($R_{acc[C_{max}]}$)

- Pharmacodynamic parameters will include:
 - Absolute concentrations and change from Baseline in immunoglobulin levels (IgA, IgM, IgG, and subclasses) at Days 29 and 85
 - Absolute numbers and change from Baseline in B cell numbers and subtypes at Day 85.

4.3.3 Other Secondary Efficacy Objectives

To further assess the level of disease activity in subjects with active RA as assessed by:

- ACR 50% and 70% (ACR50 and ACR70) response at each time point
- Percent change in hsCRP from Baseline to Day 85
- Change from Baseline in Disease Activity Score based on a 28 joint count (DAS28) and hsCRP (DAS28-hsCRP) at Days 29 and 85
- Percentage of subjects with DAS28-hsCRP < 3.2 (well controlled disease) at Day 85
- Percentage of subjects with DAS28-hsCRP < 2.6 at Day 85
- Change from Baseline in erythrocyte sedimentation rate (ESR), anti-cyclic citrullinated peptide (anti-CCP) antibody, and rheumatoid factor (RF) at Days 29 and 85
- Change from Baseline to Day 85 in a subject's self-assessments including:
 - Global assessment of disease activity
 - Self-assessment of pain
 - Self-assessment of disability (Health Assessment Questionnaire – Disability Index; HAQ-DI)
- Change from Baseline to Day 85 in Physician's Global Assessment of Disease Activity.

4.4 Exploratory Objectives

CCI

4.5 Open-label Extension Objectives

To evaluate the on-going safety and efficacy of M2951 in an open-label extension with treatment at 50 mg bid for an additional 6 months.

5 Investigational Plan

5.1 Overall Trial Design and Plan

This is a Phase IIa randomized, double-blind, placebo-controlled trial in approximately 64 subjects 18 to 75 years of age with RA on stable MTX background therapy.

Total duration of subject participation is approximately between 5 months (20 weeks) to 11 months (46 weeks), which includes:

- Screening: 28 days (4 weeks)
- Treatment: 84 days (12 weeks)
- Optional 6-month open-label extension period (26 weeks)
- Safety Follow-Up: 28 days (4 weeks)

After completing the 12-week treatment period, subjects will be offered the opportunity to participate in an optional 6-month open-label extension period where all subjects will receive M2951. For subjects who choose to participate in the optional extension period, the duration of participation will last a total of approximately 11 months.

Subjects who continue to receive M2951 during the extension period will also be required to undergo the Safety Follow-up Visit scheduled for approximately 28 days after the last treatment visit.

Screening will occur over Day -28 to -1 (Visit 1), during which time all Screening assessments must be completed and reviewed.

On Day 1 (Visit 2), after confirmation of eligibility, assessment of RA disease activity and vital signs, and obtaining of required blood and urine samples, subjects will be randomly assigned 1:1 to receive M2951 or placebo in combinations with MTX. **CCI**

Blood and urine samples will be obtained for safety (hematology, biochemistry, coagulation, and urinalysis), markers of disease activity (hsCRP, ESR, anti-CCP, and RF), PK (M2951 concentration), and PD (immunoglobulin levels, **CCI**, and B cell numbers) following the schedule detailed in the Schedule of Assessments ([Table 1](#)).

CCI

Subjects will self-administer the IMP at a set time each day (\pm 2 hours). Subjects must take their daily dose more than 1 hour prior to a meal or snack or more than 2 hours after a meal or snack. Clear fluids are allowed at any time. On trial visit days, the IMP will be administered during the trial visit after the trial visit procedures (other than PK/PD sampling) are completed.

[figure not shown]
Subjects will have trial visits weekly for the first 3 weeks of treatment; bi-weekly up until 8 weeks of treatment; a final On-Treatment Visit on Day 85 (12 weeks), and then return for 1 Follow-Up Visit approximately 28 days (4 weeks) after the last dose of IMP.

The optional Extension Period includes four scheduled visits (Visits 9, 10, 11, and 12), which correspond with Day 14, and the end of Months 1, 3, and 6. Subjects will also attend a Safety Follow-Up Visit approximately 28 days after the last dose of IMP.

The IDMC will meet at times to be laid out in the IDMC charter during the trial to monitor the safety of participants throughout the trial.

A schematic presentation of the trial design is presented in [Figure 1](#).

Figure 1 Schematic of the Trial Design

^a All subjects, whether not entering the optional open-label extension period, continuing on to the open-label extension period, or early terminating from the study will attend a Safety Follow-up Visit approximately 28 days after the last dose of IMP.

^b Subjects who decide to participate in the optional open-label extension period will sign a consent form at Visit 8, which will be considered Day 1 of the optional extension period.

^c Corresponds to the days (D) or months (M) during open-label extension period.
Bid=twice daily, OLE=open-label extension.

5.2 Discussion of Trial Design

This will be a double-blind trial. Eligible subjects will be randomized to treatment with M2951 or placebo. The 50 mg bid dose of M2951 was selected for this trial based on the results from the first-in-man trial in healthy subjects.

The primary objective of this trial is to assess the efficacy of M2951 in subjects with active RA on stable MTX background therapy as measured by the ACR20 over Day 85 of treatment. The key secondary objective is to evaluate the level of disease activity at Day 29 in subjects with active RA as assessed by percent change in hsCRP from Baseline to Day 29.

An open-label extension of 6 months duration will be offered to subjects completing the initial 12-week treatment period. The purpose is to allow all subjects the opportunity to be on active treatment with M2951 and to collect longer term safety data.

Other secondary objectives are to assess the safety and tolerability of M2951 and to evaluate the PK and PD of M2951 in subjects with RA on stable MTX background therapy.

CCI

CCI

The results of this trial will provide additional information to support dose range selection for relevant BTK occupancy for use in the future development in the RA population.

5.2.1 Inclusion of Special Populations

Not applicable.

5.3 Selection of Trial Population

Only subjects meeting all inclusion criteria and no exclusion criteria may be enrolled into the trial. Prior to performing any trial assessments not part of the subject's routine medical care, the Investigator will ensure that the subject has provided written informed consent following the procedure described in Section 9.2.

5.3.1 Inclusion Criteria

The current trial will enroll subjects who fulfill the following:

1. Men or women 18 to 75 years of age at the time of informed consent signature
2. Confirmed diagnosis of RA according to 2010 American College of Rheumatology (ACR)/The European League Against Rheumatism (EULAR) RA classification criteria of at least 6 months duration

CCI

CONFIDENTIAL
INFORMATION

30/106

3. Positive RF and/or anti-CCP
4. Persistently active disease defined as ≥ 6 swollen joints (of 66 counted) and ≥ 6 tender joints (of 68 counted)
5. hsCRP ≥ 3.6 mg/L
6. Treatment for ≥ 12 weeks with 10 to 25 mg/week MTX at a stable dose for at least 4 weeks prior to dosing with the IMP and maintained throughout the trial
7. Women of childbearing potential must use a highly effective method of contraception combined with one supplementary barrier method for 4 weeks prior to randomization, throughout the trial, and for 90 days after the last dose of IMP. For the purposes of this trial:
 - Females who are postmenopausal (age-related amenorrhea ≥ 12 consecutive months and increased follicle-stimulating hormone [FSH] > 40 mIU/mL), or who have undergone hysterectomy or bilateral oophorectomy are exempt from pregnancy testing. If necessary to confirm postmenopausal status, an FSH will be drawn at Screening
 - The definition of highly effective contraception includes:
 - combined (estrogen and progestogen containing) hormonal contraception associated with inhibition of ovulation; oral, intravaginal or transdermal
 - progestogen-only hormonal contraception associated with inhibition of ovulation; oral, injectable or implantable
 - intrauterine device (IUD)
 - intrauterine hormone-releasing system (IUS)
 - bilateral tubal occlusion
 - vasectomized partner
 - sexual abstinence
 - Supplementary barrier methods include:
 - male or female condom with or without spermicide
 - cap, diaphragm or sponge with spermicide
8. Men must agree to use and to have their female partners use a highly effective method of contraception combined with one supplementary barrier method as defined above for at least 90 days after the last IMP administration.
9. Women of childbearing potential must have a negative serum pregnancy test at the Screening Visit and a negative urine pregnancy test at Day 1/randomization before dosing
10. History of vaccinations as follows: 1) against Streptococcus pneumoniae with PPSV23 or PCV13 with repeat administration as necessary to be up to date as per local guidelines; and 2) against influenza virus (as seasonally required); or vaccination against these pathogens during Screening. Subjects receiving 1 or more of these vaccinations during Screening must have at least 2 weeks between the vaccination(s) and the date of randomization

11. Signed and dated informed consent indicating that the subject has been informed of all the pertinent aspects of the trial prior to enrollment and will comply with the requirements of the protocol.

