Change from Baseline to Month 6 in Physician's Global Assessment of Disease Activity (VAS).

Diagnosis and key inclusion and exclusion criteria:

The current trial will enroll subjects who fulfill the following key inclusion criteria:

- Men or women 18 to 75 years of age at the time of informed consent signature
- Confirmed diagnosis of RA according to 2010 American College of Rheumatology (ACR)/The European League Against Rheumatism (EULAR) RA classification criteria of at least 6 months duration
- Positive RF and/or anti-CCP (anti-cyclic citrullinated peptide)
- Persistently active disease defined as ≥ 6 swollen joints (of 66 counted) and ≥ 6 tender joints (of 68 counted)
- hsCRP ≥ 3.6 mg/L
- Treatment for ≥ 12 weeks with 10 to 25 mg/week MTX at a stable dose for at least 4 weeks prior to dosing with the IMP and maintained throughout the trial
- Women of childbearing potential must use a highly effective method of contraception combined with one supplementary barrier method for 4 weeks prior to randomization, throughout the trial, and for 90 days after the last dose of IMP. For the purposes of this trial:
 - Females who are postmenopausal (age-related amenorrhea ≥ 12 consecutive months and increased follicle-stimulating hormone [FSH] > 40 mIU/mL), or who have undergone hysterectomy or bilateral oophorectomy are exempt from pregnancy testing. If necessary to confirm postmenopausal status, an FSH will be drawn at Screening
 - The definition of highly effective contraception includes:
 - combined (estrogen and progestogen containing) hormonal contraception associated with inhibition of ovulation; oral, intravaginal or transdermal
 - progestogen-only hormonal contraception associated with inhibition of ovulation; oral, injectable, implantable
 - intrauterine device (IUD)
 - intrauterine hormone-releasing system (IUS)
 - bilateral tubal occlusion
 - vasectomized partner
 - sexual abstinence
 - Supplementary barrier methods include:
 - male or female condom with or without spermicide
 - cap, diaphragm or sponge with spermicide

- Women of childbearing potential must have a negative serum pregnancy test at the Screening Visit and a negative urine pregnancy test at Day 1/randomization before dosing.

Subjects who fulfill any of the following key exclusion criteria should not be enrolled into this trial:

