6.2 Dosage and Administration

During the 12-week treatment period, subjects will receive 50 mg bid M2951 or placebo administered as 2 matching oral capsules twice daily for 84 days. Subjects will self-administer the IMP at a set time each day (\pm 2 hours). Subjects must take their daily dose more than 1 hour prior to a meal or snack and more than 2 hours after a meal or snack. Clear fluids are allowed at any time. On trial visit days, the IMP will be administered during the trial visit after the scheduled trial visit procedures (other than post-treatment PK/PD sampling and post-treatment ECGs) are completed.

After completing the treatment period, subjects will be offered the opportunity to participate in an optional 6-month M2951 extension period on Day 85 (Visit 8). Subjects who received M2951 during the treatment period will continue with the same dose of M2951 (in tablet formulation). All subjects in the placebo group during the treatment period will discontinue placebo and start

treatment with 50 mg bid M2951 tablets on Day 85/Day 1 of OLE. On trial visit days, the IMP will be administered during the trial visit after the scheduled trial visit procedures are completed. Subjects will take 2 matching oral tablets twice daily for 6 months. Subjects will self-administer the IMP at a set time each day (\pm 2 hours). Subjects must take their daily dose more than 1 hour prior to a meal or snack and more than 2 hours after a meal or snack. Clear fluids are allowed at any time. On trial visit days, the IMP will be administered during the trial visit after the scheduled trial visit procedures are completed.

If a dose is missed, the subject can take the missed dose up to 6 hours after the scheduled time. If more than 6 hours have elapsed since the dose was missed, the subject should skip the dose for that period, make note of the missed dose, and take the next dose at the regularly scheduled time.

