7.1.3 Optional Extension Period

After completing the treatment period (Visits 2 through 8), subjects will be offered the opportunity to participate in an optional 6-month M2951 extension period. Subjects electing to participate in the Extension Period will sign an ICF at Visit 8. Subjects who received M2951 during the treatment period will continue with M2951. Subjects who received placebo during the treatment period will discontinue placebo and start treatment with M2951 on Day 85/Day 1 of OLE. The End of Treatment Visit during the treatment period (Visit 8) will be considered Day 1 of the optional extension period.

The Optional Extension Period includes four scheduled visits (Visits 9, 10, 11, and 12), which correspond with Day 14, and the end of Months 1, 3, and 6. Subjects who signed the additional ICF at Visit 8 will undergo the Optional Extension Period assessments as described in the Schedule of Assessments ([Table 1](#)).

If a subject discontinues early from the optional extension period, he/she should complete the Safety Follow-Up Visit.

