10.5 Changes to the Clinical Trial Protocol

Changes to the clinical trial protocol will be documented in writing. Substantive amendments will usually require submission to the Health Authorities and to the relevant IEC/IRB for approval or favorable opinion. In such cases, the amendment will be implemented only after approval or favorable opinion has been obtained.

Minor (nonsubstantial) protocol amendments, including administrative changes, will be filed by the Sponsor and at the site. They will be submitted to the relevant IEC/IRB or to Health Authorities only where requested by pertinent regulations. Any amendment that could affect the subject's agreement to participate in the trial requires additional informed consent prior to implementation following the process as described in Section 9.2.

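### Inclusion criterion 8 gives men a contraception period after the last dose only and does not say that it applies during dosing

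*Protocol*

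**What the plan says.** Criterion 8 in Protocol Section 5.3.1 applies to men and, through them, to their female partners. It requires a highly effective method "combined with one supplementary barrier method as defined above for at least 90 days after the last IMP administration". That is the only period it gives.

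Criterion 7, for women of childbearing potential, requires the same combination of methods "for 4 weeks prior to randomization, throughout the trial, and for 90 days after the last dose of IMP". It also contains the lists of acceptable highly effective and barrier methods.

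The Synopsis repeats the female rule ("Women of childbearing potential must use a highly effective method of contraception combined with one supplementary barrier method for 4 weeks prior to randomization", continuing with the same periods) and has no male counterpart among its key criteria.

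The list of important potential risks in Section 3.1 ends with "atrial fibrillation, drug-drug interactions, and embryofetal toxicity".

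**The concern.** The two criteria sit next to each other and serve the same purpose, but only the female one names the time on treatment. A man who agrees to contraception solely after his last dose meets criterion 8 as written, and a site has no explicit text on which to ask for more.

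What is at stake is participant and partner safety, not inference. A drug with a listed embryofetal risk should not depend on each of about 50 sites in 10 countries supplying the missing period for itself. The extension lengthens the time concerned. It also brings in men from the placebo arm, who receive M2951 for the first time on Day 85.

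**Working it through.** There is no planned figure to reproduce. The check is a comparison of texts, followed by simple day counts.

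**Step 1: criteria 7 and 8 side by side.**

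| Period | Women (criterion 7) | Men (criterion 8) |
|---|---|---|
| Before randomization | 4 weeks | not stated |
| During the trial | stated | not stated |
| After last dose | 90 days | at least 90 days |

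**Step 2: does the back-reference in criterion 8 import the female period?** The natural reading is that it does not. What criterion 7 defines is the set of methods. Had the back-reference also carried over the timing, criterion 8 would not have needed to give its own 90 days.

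**Step 3: does other text fill the gap?**

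- Synopsis: female criterion only. It lists key criteria, so the absence of a male one proves nothing by itself, but it does not help either.
- Section 7.1.3 (Optional Extension Period): no contraception period for anyone.
- Section 7.4.2 (Pregnancy and In Utero Drug Exposure): pregnancies in partners of male subjects must be recorded and notified if conceived within the adverse event reporting period, which Section 7.4.1.3 runs from consent to the Safety Follow-Up/End of Trial Visit. This is a reporting duty and does not require prevention.
- Section 7.4.3: pregnancy testing of women only.
- SAP Appendix 3, PDEV08: no period stated. The deviation is raised only if the criterion is ticked No, so it would not detect a man who agreed to post-dose contraception alone.

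**Step 4: days on M2951 that the literal phrase does not cover.** Inputs:

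- Double-blind dosing is "administered as 2 matching oral capsules twice daily for 84 days" (Section 6.2).
- The optional extension lasts 26 weeks (Section 5.1), so 26 × 7 = 182 days.
- Placebo men switch at the start of the extension: "Subjects who received placebo during the treatment period will discontinue placebo and start treatment with M2951 on Day 85/Day 1 of OLE" (Section 7.1.3).

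| Man's path | Calculation | Days on M2951 |
|---|---|---|
| M2951 arm, no extension | 84 | 84 |
| M2951 arm, completes extension | 84 + 182 | 266 |
| Placebo arm, completes extension | 0 + 182 | 182 |
| Placebo arm, no extension | 0 | 0 |

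The table counts days on active drug because that is where an embryofetal risk could arise. The criterion itself is tied to IMP, which Section 6 defines to include placebo. Counted as IMP days, the omission is the same in both arms: 84 without the extension and 266 with it.

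**The case against.** The best reply is that the literal reading is strained. It would have men use two methods for 90 days after stopping the drug and none while taking it. Criterion 8 is an entry criterion to which a man agrees before dosing. A rule with a stated end and a minimum length is most naturally understood as running continuously from that agreement. The partner-pregnancy reporting rule points the same way, since it treats conception during dosing as a matter of concern.

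Further, the information sheet, the consent forms, the Investigator's Brochure and its guidance for investigators are not available here and may give the instruction plainly. Section 3.1 describes embryofetal toxicity in general terms and does not mention exposure through the male partner. The day counts are simply treatment durations, and nothing in the documents allows the risk to be sized.

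Most of this stands as a statement of probable intent and of the limits on any claim of harm. It does not supply the missing words. A reproductive-safety rule that is explicit for women should be explicit for men too, and a confident guess at the intent is a reason to write it down. The point about unseen documents affects how far the gap reached participants, but not whether the protocol text contains it.

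**Conclusion.** The concern holds. Criterion 8 states a post-treatment period only, and nothing else readable in the protocol or SAP gives men an on-treatment requirement. Followed to the letter, it leaves the whole dosing period uncovered: up to 266 days on M2951 for a man in the active arm who completes the extension.

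That figure assumes full 84-day and 182-day dosing and measures the gap in the wording. It is not an estimate of unprotected exposure. The number of male subjects is not given, no harm is shown, and the consent forms may already state the period. Confidence is high that the period is missing from the text; the documents give no basis for judging its consequences.

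This should be corrected as a matter of participant safety. It has no bearing on the trial's statistical conclusions.

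**What to change.** In criterion 8, insert immediately before the existing 90-day phrase: *from first IMP administration, throughout the trial (including the open-label extension), and*. Check the main and extension consent forms, and align them if they do not already say this.

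The cost is a small protocol amendment. Under Section 10.5, any amendment that could affect a subject's "agreement to participate in the trial requires additional informed consent prior to implementation", so men already enrolled may need to be re-consented if the clarified period is new to them. If the consent forms already state it, the amendment only brings the protocol into line with them. Endpoints, sample size, power and analyses do not change.
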